5.4. Subgroups

Subgroup analyses of safety will be performed for the following patient demographics and other factors.

- Hepatic impairment
- Renal impairment
- Children (<15 years), adults (≥ 15 to < 65 years), elderly (≥ 65 years)
- Age [< 65 years, ≥ 65 to < 70 years, ≥ 70 to < 75 years, ≥ 75 to < 80 years, ≥ 80 to < 85 years, ≥ 85 years]
- Sex [male, female]
- Inpatient/outpatient status at the initial prescription [inpatient, outpatient]
- Body weight at the start of treatment (by sex) [< 40 kg, ≥ 40 to < 50 kg, ≥ 50 to < 60 kg, ≥ 60 kg]
- Name of target disease (i.e., diagnosis of neuropathic pain) [by disease name]
- Hemodialysis [no, yes]
- Creatinine clearance [< 15 mL/min, ≥ 15 to < 30 mL/min, ≥ 30 to < 60 mL/min, ≥ 60 mL/min]
- Past medical history [no, yes]
- Complications [no, yes]
- Prior medications [no, yes]
- Concomitant medications [no, yes]
- Non-medication therapies [no, yes]
- Timing of drug administration (at the start of treatment) [before meal, after meal, other]
- Daily dose (at the start of treatment) [≤ 25 mg, > 25 to ≤ 75 mg, > 75 to ≤ 150 mg, > 150 to ≤ 300 mg, > 300 to ≤ 600 mg, > 600 mg]
- Daily dose (maximum) [≤ 25 mg, > 25 to ≤ 75 mg, > 75 to ≤ 150 mg, > 150 to ≤ 300 mg, > 300 to ≤ 600 mg, > 600 mg]
- Pregnant and parturient women (pregnant)

Subgroup analyses of efficacy will be performed for the following patient demographics and other factors.

- Hepatic impairment
- Renal impairment
- Children (<15 years), adults (≥ 15 to < 65 years), elderly (≥ 65 years)
- Age [< 65 years, ≥ 65 to < 70 years, ≥ 70 to < 75 years, ≥ 75 to < 80 years, ≥ 80 to < 85 years, ≥ 85 years]
- Sex [male, female]

- Inpatient/outpatient status at the initial prescription [inpatient, outpatient]
- Body weight at the start of treatment (by sex) [<40 kg, ≥ 40 to <50 kg, ≥ 50 to <60 kg, ≥ 60 kg]
- Name of target disease (i.e., diagnosis of neuropathic pain) [by disease name]
- Hemodialysis [no, yes]
- Creatinine clearance [<15 mL/min, ≥ 15 to <30 mL/min, ≥ 30 to <60 mL/min, ≥ 60 mL/min]
- Past medical history [no, yes]
- Complications [no, yes]
- Prior medications [no, yes]
- Concomitant medications [no, yes]
- Timing of drug administration (at the start of treatment) [before meal, after meal, other]
- Daily dose (at the start of treatment) [≤ 25 mg, >25 to ≤ 75 mg, >75 to ≤ 150 mg, >150 to ≤ 300 mg, >300 to ≤ 600 mg, >600 mg]
- Daily dose (maximum) [≤ 25 mg, >25 to ≤ 75 mg, >75 to ≤ 150 mg, >150 to ≤ 300 mg, >300 to ≤ 600 mg, >600 mg]

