8.2.2. Patient demographics and treatment history

- **Patient demographics**

The following patient demographics will be tabulated in the safety analysis set and efficacy analysis set in accordance with Section 8.1.

- Sex [male, female]

- Age at the start of treatment (continuous data)
- Age category at the start of treatment [<15 years, ≥ 15 to <65 years, ≥ 65 years]
- Age category at the start of treatment [<65 years, ≥ 65 to <70 years, ≥ 70 to <75 years, ≥ 75 to <80 years, ≥ 80 to <85 years, ≥ 85 years]
- Inpatient/outpatient status at the initial prescription [inpatient, outpatient]
- Height at the start of treatment (by sex) (continuous data)
- Body weight at the start of treatment (by sex) (continuous data)
- Body weight category at the start of treatment (by sex) [<40 kg, ≥ 40 to <50 kg, ≥ 50 to <60 kg, ≥ 60 kg]
- Name of target disease (i.e., diagnosis of neuropathic pain) [by disease name]
- Duration of target disease (i.e., diagnosis of neuropathic pain) (continuous data)
- Severity of target disease (i.e., diagnosis of neuropathic pain) [mild, moderate, severe]
- Pain score (continuous data)
- Name of underlying disease (i.e., primary disease of nerve damage that cause neuropathic pain) [by disease name]
- Hepatic impairment [no, yes (mild, moderate, severe)]
- Renal impairment [no, yes (mild, moderate, severe)]
- Hemodialysis [no, yes]
- Creatinine clearance category [<15 mL/min, ≥ 15 to <30 mL/min, ≥ 30 to <60 mL/min, ≥ 60 mL/min]
- Hyperalgesia [no, yes]
- Past medical history [no, yes]
- Complications [no, yes]

The following number and proportion of patients will be tabulated by SOC and PT in the safety analysis set.

- Breakdown of underlying disease
- Breakdown of past medical history
- Breakdown of complications

The following number and proportion of patients will be tabulated in the safety analysis set and efficacy analysis set.

- Presence or absence and breakdown of concomitant medications
- Presence or absence and breakdown of concomitant non-medication therapies
- Presence or absence and breakdown of prior medications

If patient demographics are tabulated by subgroup based on the initial dose specified in Section 5.4, the following will be tabulated in the safety analysis set and efficacy analysis set in accordance with Section 8.1.

- Age at the start of treatment (continuous data)

- Age category at the start of treatment [<15 years, ≥ 15 to <65 years, ≥ 65 years]

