- Age category at the start of treatment [<65 years, ≥ 65 to <70 years, ≥ 70 to <75 years, ≥ 75 to <80 years, ≥ 80 to <85 years, ≥ 85 years]
- Body weight at the start of treatment (by sex) (continuous data)
- Body weight category at the start of treatment (by sex) [<40 kg, ≥ 40 to <50 kg, ≥ 50 to <60 kg, ≥ 60 to <70 kg, ≥ 70 to <80 kg, ≥ 80 to <90 kg, ≥ 90 to <100 kg, ≥ 100 kg]
- Duration of target disease (i.e., diagnosis of neuropathic pain) (continuous data)
- Severity of target disease (i.e., diagnosis of neuropathic pain) [mild, moderate, severe]
- Name of underlying disease (i.e., primary disease of nerve damage that cause neuropathic pain) [by disease name]
- Hepatic impairment [no, yes (mild, moderate, severe)]
- Renal impairment [no, yes (mild, moderate, severe)]
- Hemodialysis [no, yes]
- Creatinine clearance (continuous data)
- Creatinine clearance category [<15 mL/min, ≥ 15 to <30 mL/min, ≥ 30 to <60 mL/min, ≥ 60 mL/min]
- Past medical history [no, yes]
- Complications [no, yes]
- Past medical history or complications of cardiovascular disorder^a [no, yes]
- Past medical history of angioedema^b [no, yes]
- Past medical history or complications (at the start of treatment): Peripheral edema and edema-related events^c [no, yes]
- Past medical history or complications (at the start of treatment): Dizziness, somnolence, loss of consciousness, syncope, and potential for accidental injury^c [no, yes]
- Past medical history or complications (at the start of treatment): Vision-related events^c [no, yes]
- Concomitant medications (at the start of treatment) [no, yes]
- Concomitant use of analgesics^d (at the start of treatment) [no, yes]

^a: Past medical history or complications coded to the MedDRA SOC “Cardiac disorders” or “Vascular disorders”

^b: Past medical history coded to the MedDRA HLT “angioedemas”

^c: The same definition as the major investigation items

^d: The following analgesics will be considered as candidates and identified: drugs classified as “3 digits, 114 antipyretics, analgesics, and anti-inflammatory agents; 3 digits, 113 antiepileptics” in the drug name data file or drugs classified as “Standardised Drug Groupings (SDG), analgesia producing opioids; ATC 3rd level, N06A (ANTIDEPRESSANTS)” in the WHO-drug dictionary.

- Concomitant use of opioid analgesics^a (at the start of treatment) [no, yes]
- Concomitant use of oxycodone or lorazepam^b (at the start of treatment) [no, yes]

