- Concomitant use of drugs causing angioedema^c (at the start of treatment) [no, yes]
- Concomitant use of thiazolidines^d (at the start of treatment) [no, yes]

• Information on administration of Lyrica

The following information on administration of Lyrica will be tabulated in the safety analysis set.

- Duration of administration [\leq 4 weeks, $>$ 4 to \leq 13 weeks, $>$ 13 weeks]
- Timing of administration (at the start of treatment) [morning, noon, evening, bedtime, other]
- Timing of drug administration (at the start of treatment) [before meal, after meal, other]
- Daily dose (continuous data)
- Daily dose (at the start of treatment) [\leq 25 mg, $>$ 25 to \leq 75 mg, $>$ 75 to \leq 150 mg, $>$ 150 to \leq 300 mg, $>$ 300 to \leq 600 mg, $>$ 600 mg]
- Daily dose (maximum) [\leq 25 mg, $>$ 25 to \leq 75 mg, $>$ 75 to \leq 150 mg, $>$ 150 to \leq 300 mg, $>$ 300 to \leq 600 mg, $>$ 600 mg]
- Daily dose (final) [\leq 25 mg, $>$ 25 to \leq 75 mg, $>$ 75 to \leq 150 mg, $>$ 150 to \leq 300 mg, $>$ 300 to \leq 600 mg, $>$ 600 mg]

Dosing period is from the day of initial dose in the survey to the day of last dose, including period of dose interruption. Daily dose (continuous data) will be calculated as the mean dosage during the entire period in which Lyrica was actually administered to each patient excluding pro re nata (PRN) prescription, and the mean, standard deviation, and mode will be calculated in the safety analysis set.

^a: The following opioid analgesics will be considered as candidates and identified: drugs classified as “Standardised Drug Groupings (SDG), analgesia producing opioids” in the WHO-drug dictionary.

^b: Drugs classified as “7 digits, 8119002 oxycodone hydrochloride hydrate or 1124022 lorazepam” in the drug name data file

^c: The following drugs causing angioedema will be considered as candidates and identified: drugs classified as “4 digits, 6111 penicillins; 3 digits, 254 contraceptives” in the drug name data file or drugs classified as “Standardised Drug Groupings (SDG), non-steroidal anti-inflammatory drugs (NSAIDs); ACT 3rd level, C09A (ACE INHIBITORS, PLAIN), C09B (ACE INHIBITORS, COMBINATIONS), C09C (ANGIOTENSIN II ANTAGONISTS, PLAIN), C09D (ANGIOTENSIN II ANTAGONISTS, COMBINATIONS); ACT 3rd level, B01AD (Enzymes)” in the WHO-drug dictionary.

^d: Drugs with non-proprietary name of pioglitazone in the drug name data file

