For “peripheral edema and edema-related events”, number and proportion of patients with events will be tabulated by presence or absence of weight increase. Two types of definitions of patients with weight increase are used: 1) those with “weight increased (MedDRA PT)” reported as an adverse reaction; 2) those with body weight increased by 7% or more from baseline at least once. Number and proportion of patients with adverse reactions will be tabulated for each SOC and PT by presence or absence of peripheral edema. In addition, number and proportion of patients with the following adverse reactions will be tabulated by presence or absence of peripheral edema to evaluate the relationship between peripheral edema and cardiovascular and respiratory events.

- Events coded to the MedDRA PT “arrhythmia”, “atrial fibrillation”, “cardiovascular disorder”, “cardiac failure congestive”, “hypertension”, “hypotension”, “palpitations”, “tachycardia”, or “dyspnoea”
- Events coded to the MedDRA SOC “Cardiac disorders”, “Vascular disorders”, or “Respiratory, thoracic and mediastinal disorders”

For “dizziness, somnolence, loss of consciousness, syncope, and potential for accidental injury”, number of days to onset will be tabulated using more specific categories (≤ 4 weeks [1 to 28 days], 1 to 7 days, 8 to 14 days, 15 to 21 days, 22 to 28 days; >4 weeks [≥ 29 days], >4 to ≤ 13 weeks, >13 weeks). In addition, number and proportion of patients with adverse reactions will be tabulated by factor specified in Section 5.4. Tests specified in Section 8.1.3 will be performed to evaluate the relationship between patient demographics, etc. and development of adverse reactions.

Moreover, the median number of days to onset will be tabulated for the following adverse reactions.

- Dizziness
- Somnolence

^a: Occurrence of cardiovascular and respiratory events will be examined in patients with peripheral edema and edema-related events.

- Peripheral edema and edema-related events
- **Pancreas-related events, thyroidal function-related events, change in appetite and activity-related events, suicide-related events, withdrawal symptom and rebound phenomenon-related events, and skin disorder-related events**

Number and proportion of patients will be calculated for each event.

- **Patients with special background**

Number and proportion of patients with adverse reactions and serious adverse reactions will be calculated by SOC and PT in the following subgroups and other patients.

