8.2.3.3. Other endpoints

- **Body weight**

Summary statistics specified in Section 8.1.1 will be calculated by time point as defined in Appendix 1 for measurements and their changes from baseline.

Number and proportion of patients with the following adverse reactions will be tabulated for patients whose body weight increased by 7% or more from baseline at least once and other patients.

- Abnormal glucose tolerance-related events: Events coded to the MedDRA HLGT “glucose metabolism disorders (incl diabetes mellitus)” or the MedDRA HLT “carbohydrate tolerance analyses (incl diabetes)”
- Dyslipidemia-related events: Events coded to the MedDRA HLGT “lipid metabolism disorders” or “lipid analyses”
- Events coded to the MedDRA PT “arrhythmia”, “atrial fibrillation”, “cardiovascular disorder”, “cardiac failure congestive”, “hypertension”, “hypotension”, “palpitations”, “tachycardia”, or “dyspnoea”
- Events coded to the MedDRA SOC “Cardiac disorders”, “Vascular disorders”, or “Respiratory, thoracic and mediastinal disorders”

- **Laboratory parameters**

Summary statistics specified in Section 8.1.1 will be calculated by time point as defined in Appendix 1 for laboratory parameters and their changes from baseline.

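### The table relating peripheral edema to cardiovascular and respiratory reactions is not split by pre-existing cardiovascular disease, so baseline disease may appear as a link with edema on Lyrica

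*SAP*

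**What the plan says.** - **The edema table.** SAP 8.2.3.1, under the major investigation items, counts patients with nine listed cardiovascular and respiratory preferred terms, and with any reaction in the cardiac, vascular or respiratory organ classes, "by presence or absence of peripheral edema to evaluate the relationship between peripheral edema and cardiovascular and respiratory events". No further split, test, ratio or interval is specified.
- **The weight-gain table.** SAP 8.2.3.3 has the same cardiovascular and respiratory rows, plus glucose and lipid rows. They "will be tabulated for patients whose body weight increased by 7% or more from baseline at least once and other patients". No purpose is stated for this table.
- **The baseline flags.** SAP 8.2.2 defines "Past medical history or complications of cardiovascular disorder" (footnote a: cardiac or vascular organ class) and "Concomitant use of thiazolidines" at the start of treatment (identified as pioglitazone). Both stand in a list introduced by "If patient demographics are tabulated by subgroup based on the initial dose specified in Section 5.4", and the SAP gives them no other use.
- **The general factors.** SAP 5.4 has medical history and complications only as any/none. Neither edema nor weight gain is a 5.4 factor, so the background tables by subgroup in 8.2.3.4 do not reach them. SAP 6.4 names no covariates.
- **The protocol's intention.** Protocol section 1 marks cardiovascular and respiratory events as an add-on to the edema item. Protocol 6.9 says that the occurrence of edema will be examined by dose, concomitant therapy and background variables. The SAP writes out by-factor tables and tests only for the dizziness item (8.2.3.1) and for any adverse reaction (8.2.3.4).

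**The concern.** The survey has no control group, so edema versus no edema is the only contrast available for this question. Patients who start with heart or vascular disease may be more likely to develop edema and also more likely to have a cardiovascular or respiratory reaction. The two-group table cannot separate that explanation from a relationship between the reactions and edema on treatment.

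The question matters to the sponsor. Protocol 6.9 motivates it by the package insert's heart-failure precaution and by more hypertension and dyspnea among edema patients in earlier overseas studies. The results go into the reexamination application and into proper-use information. The plan already derives the variable that would show whether baseline disease is at work, but does not apply it here.

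**Working it through.** **Plan's own figures.** The documents state none for this table. The survey size is the 3400 target, whose stated detection probability reproduces: 1 − 0.999^3400 = 0.967, against 97%. It is not affected by this point.

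**Inputs.** N = 3400 is from the documents. All other inputs are assumptions, because the documents give no baseline prevalence and no edema or cardiovascular reaction rates:

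- p: share of patients with the cardiovascular flag
- e1, e0: risk of edema with and without the flag
- c1, c0: risk of a cardiovascular/respiratory reaction with and without the flag
- no association between edema and reaction within either stratum (within-stratum ratio set to 1)

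**Formulas.**

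- Edema share: E = p·e1 + (1 − p)·e0
- Flagged share among edema patients: h1 = p·e1 / E
- Flagged share among the others: h0 = p·(1 − e1) / (1 − E)
- Reaction risk in each group: r = h·c1 + (1 − h)·c0
- Crude ratio: r1 / r0
- Approximate 95% interval: exp[ln(ratio) ± 1.96·√(1/a − 1/n1 + 1/c − 1/n0)], where a and c are the expected events and n1 and n0 the group sizes

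**One case in full** (p = 0.40, e0 = 0.05, e1 = 0.15, c0 = 0.01, c1 = 0.05):

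- E = 0.06 + 0.03 = 0.09, so 306 patients with edema and 3094 without
- h1 = 0.06/0.09 = 0.667; h0 = 0.34/0.91 = 0.374
- r1 = 0.667 × 5% + 0.333 × 1% = 3.67%; r0 = 0.374 × 5% + 0.626 × 1% = 2.49%
- Crude ratio 1.47
- Events with edema: 306 × 3.67% = 11.2, against 7.6 at the no-edema risk

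**Higher reaction rate (c0 = 1%).**

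| p | e0 → e1 | c0 → c1 | Edema patients | Events in them | Expected at no-edema risk | Crude ratio (approx. 95% interval) |
|---|---|---|---|---|---|---|
| 0.40 | 5% → 10% | 1% → 3% | 238 | 5.1 | 4.2 | 1.21 (0.49–2.96) |
| 0.40 | 5% → 15% | 1% → 5% | 306 | 11.2 | 7.6 | 1.47 (0.79–2.72) |
| 0.30 | 4% → 12% | 1% → 5% | 218 | 7.1 | 4.6 | 1.53 (0.71–3.27) |

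The excess is 0.9, 3.6 and 2.4 patients.

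**Lower reaction rate.** With c0 = 0.5%, e0 = 5%, p from 10% to 40%, edema 2 to 3 times and reactions 2 to 5 times as frequent in flagged patients, the crude ratio runs from 1.08 to 1.57, on about 1 to 6 events among edema patients. For example, p = 30% with both multiplied by 3 gives 1.06% against 0.78%, ratio 1.37, from 2.9 events.

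**When the bias vanishes.** If the flag raises only edema, or only the reaction, the crude ratio is 1.00 at every prevalence tried.

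**What the split shows.** Within each stratum the ratio returns to 1.00 by construction. The unflagged edema patients in the three tabulated cases hold 102 × 1% = 1.0, again 1.0, and 95 × 1% = 0.95 events, so about one event each.

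**The case against.** The case against is substantial, and much of it stands.

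- **Little is numerically at stake.** The excess is one to four patients and every interval spans 1. SAP 4.1 calls testing exploratory, 4.2 has no decision rule, and this table has no test or ratio. This stands, and it limits the point to presentation. It does not remove it, because the table's stated purpose is to evaluate a relationship and a crude contrast can mislead without a p-value.
- **Only reactions judged related to Lyrica are counted (SAP 6.1).** This may reduce confounding but cannot be relied on to remove it. Under protocol 7.2.1 it is enough that causality cannot be ruled out.
- **Other material gives context.** Protocol 6.4 asks for detailed entry of clinically significant changes from the pre-treatment condition in edema cases. The SAP lists major-item reactions and tabulates reactions by target disease and by drug class. With about 5 to 11 cases, individual review is a reasonable complement. None of these crosses baseline cardiovascular disease with edema.
- **The flag leaves out respiratory disease.** It covers cardiac and vascular organ classes, while the outcomes include dyspnoea and the whole respiratory class. This stands and must be stated with the table.

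A reader might carry the argument over to diabetes, weight gain and the glucose rows of 8.2.3.3. The documents do not support that. They define no diabetes-at-start flag, state no relationship purpose for that table, and do not say that diabetes raises the chance of 7% weight gain. On assumed inputs (20–25% diabetic, weight gain 3–4% in others and 1.5–2 times as frequent in diabetics, glucose reactions 2% v 0.1%), the ratio with no true link is 1.31 to 1.57. It rests on about one exposed event, with about 0.1 in the non-diabetic stratum.

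A reader might also want a Mantel-Haenszel ratio. With about one edema-group event in the unflagged stratum it would tell little, and the plan has no crude ratio for it to accompany.

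**Conclusion.** The point holds in a limited form. The edema table in SAP 8.2.3.1 has a stated relational purpose, is not split by baseline cardiovascular disease, and could be split with a flag that the SAP already defines.

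The possible distortion is a crude ratio of about 1.1 to 1.6 with no true link. It rests on assumed prevalences and rates, and on baseline disease raising both edema and the reaction. At 3400 patients the number of exposed events is small: about 5 to 11 in the higher-rate cases and fewer in the lower-rate ones.

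A reader might infer that baseline disease will show up as a link. The documents do not support that certainty: they give no rates, and if disease acts on only one of the two variables the crude ratio is 1.00. The supportable statement is that it may appear so, and that the planned table gives no means of telling. This is a worthwhile improvement to a named safety question. It is not a flaw that invalidates the analysis.

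**What to change.** In SAP 8.2.3.1:

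1. Also present the edema-by-cardiovascular/respiratory table separately for patients with and without the cardiovascular history/complication flag of 8.2.2 (footnote a).
2. Show the number of thiazolidine users at the start of treatment in the edema and no-edema groups.
3. State that the strata are descriptive, that small cells limit interpretation, and that the flag does not cover baseline respiratory disease.

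The cardiovascular and respiratory rows of the weight-gain table in 8.2.3.3 may be shown in the same way. No diabetes split of the glucose rows and no adjusted ratio is asked for.

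**Cost:** SAP wording and a few extra tables from variables already derived, with no new data collection. The downside is that the added tables will be sparse.

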**(2) Clinical findings**

The following information will be entered about the clinical findings before the start of treatment (including the first day of treatment) and during the period from the start of treatment to the day of safety evaluation. In cases where treatment has been completed or discontinued before Week 13, the data at the time of completion (discontinuation) of treatment will be entered. If the investigator considers that the change in any of the clinical findings from the pre-treatment status is abnormal, it will be reported as an adverse event.

**(2)-1 Information before the start of treatment (including the first day of treatment) and during the period from the start of treatment to the day of safety evaluation**

[Presence/absence of peripheral edema or edema in general]\*, [Presence/absence of dizziness, somnolence, loss of consciousness, syncope and potential for accidental injury], [Presence/absence of ophthalmological abnormalities], [Presence/absence of suicidal ideation (including suicide attempt and suicide after start of treatment)], [Presence/absence of pathologic changes in appetite and activity]

**Supplementary note\***: In cases where peripheral edema or edema in general is found, adverse events of the cardiovascular and respiratory systems also need to be checked. If any clinically significant change from the pre-treatment condition is found, it should be entered in detail in the field for adverse events.

**(2)-2 Information in cases of completed (discontinued) treatment with the product (information on the day of safety evaluation following 7-day period after the day of discontinuation [including Day 7 of this period])**

[Presence/absence of withdrawal symptom/rebound phenomenon]

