## 6.8 Adverse events

For evaluation of safety, the incidence of adverse events following the start of treatment with the product will be checked, and the following information will be entered. If any adverse event occurs, the investigator should take appropriate measures and immediately report it to the sponsor. When the causal relationship between the event and the product cannot be ruled out, observe the course of event or its sequela until they disappear or become stabilized at the level acceptable for the investigator and the sponsor.

A detailed investigation will be separately carried out if patients have intrauterine exposure or develop serious adverse reactions, adverse reactions not listed in the package insert and the like and the sponsor deems it necessary.

- [1] Day of safety evaluation (as a rule, day of last visit within 29 days after the start of treatment)
- [2] Presence/absence of adverse events
- [3] Name of adverse event
- [4] Date of onset
- [5] Measures taken

- [6] Seriousness
- [7] Outcome
- [8] Causal relationship to the product

[The following information should be entered if the adverse event is associated with abnormal changes in test data such as laboratory tests.]

- [1] Name of test
- [2] Reference value at the facility
- [3] Unit
- [4] Date of measurement
- [5] Results

Supplementary note: Adverse events mean all events unfavorable for the patient, arising after the start of treatment with the product, regardless of presence/absence of causal relationship to the product (including clinically significant abnormal changes in laboratory parameters). Serious adverse events mean death, life-threatening events, and events possibly causing hospitalization, extension of hospital stay period, permanent or marked disorders/disabilities, congenital anomalies/defects or other medically significant events/disorders.

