## 6.9 Major investigation items

The following events should be evaluated as major investigation items in this survey.

- [1] Peripheral edema and edema-related events
 

Information will be collected about the presence/absence of events related to peripheral edema and the course of patients before and after the onset of events. The situations on development of these events will be analyzed by means of factor analysis, including analysis of the site affected, dose of the product, concomitant therapy, background variables, etc. The package insert gives precautions on congestive heart failure in patients presenting symptoms related to edema. In 30 overseas placebo-controlled studies, the incidence of hypertension and dyspnea was higher in the patients developing peripheral edema than in patients free of peripheral edema, although the incidence of the other events did not differ markedly between these two groups. In view of these facts, information on cardiac function and the incidence of adverse events of the respiratory system will be also collected.
- [2] Dizziness, somnolence, loss of consciousness, syncope and potential for accidental injury
 

Information will be collected about the presence/absence of events related to dizziness, somnolence, loss of consciousness, syncope and potential for accidental injury and the course of patient's condition before and after the onset of events. The situations on development of these events will be analyzed by factor analysis, including analysis of the dose of the product, concomitant therapy, background variables and so on.
- [3] Vision-related events
 

Information will be collected about the presence/absence of events related to the eyes and the course of patient's condition before and after the onset of events. The situations on development of the events will be analyzed by factor analysis, including analysis of the dose of the product, concomitant therapy, background variables and so on.

Patients developing adverse events included in the major investigation items will be

separately investigated in detail if the sponsor deems it necessary.

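### The targeted cardiovascular and respiratory check is prompted by edema, so an excess of these reactions in the SAP's by-edema table may partly reflect unequal ascertainment

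*SAP*

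**What the plan says.** **Collection.** The supplementary note in Protocol 6.4(2) reads: "In cases where peripheral edema or edema in general is found, adverse events of the cardiovascular and respiratory systems also need to be checked". It continues: "If any clinically significant change from the pre-treatment condition is found, it should be entered in detail in the field for adverse events". The presence/absence findings recorded for all patients in 6.4(2) and the Section 6 schedule cover edema, the dizziness and consciousness group, the eyes, suicidal ideation, and appetite and activity. None covers the cardiovascular or respiratory system.

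Protocol 6.8 applies to every patient: "the incidence of adverse events following the start of treatment with the product will be checked, and the following information will be entered". Its definition is broad: "Adverse events mean all events unfavorable for the patient, arising after the start of treatment with the product". Protocol 6.9, under the edema item, adds that "information on cardiac function and the incidence of adverse events of the respiratory system will be also collected".

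**Analysis.** SAP 8.2.3.1 takes nine preferred terms (hypertension, palpitations and dyspnoea among them) and three system organ classes, and counts patients with these adverse reactions "by presence or absence of peripheral edema to evaluate the relationship between peripheral edema and cardiovascular and respiratory events". A footnote to the same item describes something narrower: "Occurrence of cardiovascular and respiratory events will be examined in patients with peripheral edema and edema-related events".

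**Background.** Protocol 6.9 cites a set of 30 placebo-controlled trials run overseas, in which "the incidence of hypertension and dyspnea was higher in the patients developing peripheral edema than in patients free of peripheral edema", with no marked difference for the other events.

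**The concern.** A comparison of two groups on a reported outcome needs the outcome to be sought about equally in both. Here a finding of edema sets off the extra search, and edema status then defines the columns. Palpitations, mild dyspnoea or a raised blood pressure can plausibly go unreported unless someone asks. If the prompt does anything, it raises the count in the edema column, so the bias would run towards an excess with edema.

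The stake is interpretation. The survey feeds the reexamination application, and an excess would point the same way as the overseas finding on hypertension and dyspnea. It could be read as confirmation in routine practice, although the table cannot separate a real association from the effect of the prompt. Neither document mentions or handles the difference in ascertainment.

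**Working it through.** **Plan's own figure.** Neither document gives a figure for the by-edema comparison, so there is none to reproduce. The target of 3400 is used below only to set a scale.

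**Side by side.**

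| | Edema found | No edema found |
|---|---|---|
| General adverse event collection (Protocol 6.8) | yes | yes |
| Targeted cardiovascular/respiratory check (Protocol 6.4(2) note) | yes | no instruction |
| Compared in SAP 8.2.3.1 | presence column, if the edema is peripheral | absence column |

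**Model.** Let both groups have the same true risk t. Let s1 be the probability that a reaction is captured with the prompt, s0 without it, and c = s0/s1. Assume the share of events judged related is the same in both columns, since the table counts adverse reactions. Then

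apparent risk ratio = (t × s1)/(t × s0) = 1/c, whatever t is.

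The prompt is triggered by edema in general as well as peripheral edema, while the table groups by peripheral edema. Some prompted patients may therefore sit in the absence column. If they are a share q of that column,

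apparent risk ratio = 1/(q + (1 − q) × c).

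**Results.** The documents give neither c nor q; all values are assumed.

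| c | q = 0 | q = 0.1 |
|---|---|---|
| 1.0 | 1.00 | 1.00 |
| 0.9 | 1/0.90 = 1.11 | 1/0.91 = 1.10 |
| 0.8 | 1/0.80 = 1.25 | 1/0.82 = 1.22 |
| 0.7 | 1/0.70 = 1.43 | 1/0.73 = 1.37 |
| 0.5 | 1/0.50 = 2.00 | 1/0.55 = 1.82 |

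**In patients.** Assume 10% of 3400 have edema (340 against 3060), t = 2%, s1 = 0.90, s0 = 0.60 and q = 0.

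- Edema: 340 × 0.02 × 0.90 = 6.1 patients (1.8%).
- No edema: 3060 × 0.02 × 0.60 = 36.7 patients (1.2%).
- Apparent ratio: 1.8/1.2 = 1.5 with no true association.
- With unprompted capture the edema column would show 340 × 0.02 × 0.60 = 4.1, so the prompt adds about 2 patients. The Poisson standard deviation of a count of 6.1 is √6.1 = 2.5.

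The ratio can move noticeably while the number of patients behind it stays within chance variation. That is a further reason not to read much into a difference between the columns.

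**The case against.** The strongest reply is that the protocol does not confine collection to edema patients. Section 6.8 requires all adverse events from everyone, and the 6.9 sentence on cardiac and respiratory information carries no edema condition. A reader might infer from the 6.4(2) note that these events are looked for only when edema is found. The documents do not support that: only the targeted check is tied to edema. But equal reportability is not equal capture, and a note that added nothing to ordinary reporting would have had no purpose.

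A reader might also infer that the prompt does produce part of any excess, or that the table is bound to show one. That does not follow either. No capture rate is given, there is no bias at c = 1, and the overseas result makes a genuine excess possible.

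The mismatch between trigger and grouping also stands: patients with non-peripheral edema, and possibly those with edema before treatment, may be prompted yet counted in the absence column, which dilutes any effect.

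Finally, the stakes are limited. This table has no specified test or risk ratio; the risk ratios in SAP 8.2.3.4 are for the Section 5.4 factors, and edema is not one. SAP 4.1 treats all testing as exploratory. Nor is this the survey's only look at what accompanies edema, since SAP 8.2.3.1 also crosses it with weight increase and with all reactions by SOC and PT. All of this limits the consequence; none of it makes ascertainment equal in the two columns.

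**Conclusion.** The point holds as a limit on what one descriptive table can support. Ascertainment of cardiovascular and respiratory reactions may differ between the columns, the likely direction is an excess with edema, and neither document addresses it. The size cannot be derived from the documents: the null risk ratio is about 1/c, closer to 1 with misplaced prompted patients, and exactly 1 if capture is equal. This rests on two assumptions: that the prompt can only raise capture (c no greater than 1), and that relatedness is judged alike in both groups.

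It does not show that an observed excess would be spurious. It shows that a difference between the columns would not by itself be evidence of an association, which is more than the SAP's stated purpose for the table allows. The sample size and the primary incidence of adverse reactions are not affected.

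**What to change.** In SAP 8.2.3.1, using the onset dates and seriousness already collected under Protocol 6.8:

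1. Keep the planned table and add the same by-edema table restricted to serious adverse reactions. Staying with reactions keeps the endpoint unchanged, and serious ones should depend less on a prompt.
2. Within patients with edema, split the listed reactions by onset before, or on or after, the onset of edema. Reactions that began earlier are less likely to owe their recording to the edema finding, although the check can still bring an earlier one to light.
3. Replace the stated purpose of evaluating a relationship with descriptive wording, and place a note beside the all-reaction table. For example: *The protocol asked for a targeted check of these systems where edema was found and gave no such instruction for other patients; a difference between columns is not by itself evidence of an association.*

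The cost is a few lines of SAP text and two small tables. Serious reactions will be few, so the first added table will be imprecise. The onset split has no comparator among patients without edema. No change to the survey form is proposed, because the SAP revision history records the survey as completed.
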